SELF-MANAGEMENT APP FOR PATIENTS WITH LEFT VENTRICULAR ASSIST DEVICES

STUDY PROTOCOL & STATISTICAL ANALYSIS

[name]

University of Michigan
Johns Hopkins University

NCT # ***NCT03049748***

Purpose

This study aimed to obtain preliminary efficacy data of using a mobile phone application (VAD Care App)¹ as a self-management tool in patients with left-ventricular assist devices (LVAD). The specific aim was to evaluate the effects of the app on the patient's (1) self-efficacy and (2) adherence to the LVAD care regimen; (3) complications; (4) overall health status, and (5) quality of life.

Study Design

Pilot randomized control trial. Measurements completed at baseline (T0) and months 1 (1), 3 (T2), and 6 (T3) post-hospital discharge.

Sample and Setting

This study recruited a total of 68 patients with newly implanted, non-pulsatile flow durable LVADs and from four VAD Centers in the Midwest and Northeast regions in the United States. The study was implemented in inpatient and outpatient settings of the hospitals.

Study Procedure

Recruitment and screening. A trained clinical research coordinator (CRC) conducted all recruitment and screening of study participants. Recruitment and obtaining informed consent occurred in each hospital's inpatient setting. A screening checklist based on the study inclusion and exclusion criteria (table insert) was used. Since cognitive impairment is common in heart failure, we used the 11-item Mini-Mental State Exam (MMSE) as a screening tool. The MMSE is a valid, reliable, and widely used cognitive screening tool across care settings and conditions worldwide. A score of less than 24 in the MMSE denotes cognitive impairment.^{2,3} Participation in this study also required a dedicated caregiver, a customary practice in the participating VAD centers.

Patients	
Inclusion	
• First-time LVAD implant
	
• 21 to 80 years of age
	
• 6th grade education or higher
	
• Can read and understand English
	
• Planned hospital discharge within a week of enrollment
	
• Completed LVAD care training
Exclusion	
• Blindness
	
• Inability to or refuse to use a smartphone
	
• Cannot hear alarms, and/or

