	
• Cognitively impaired documented in the medical record of an MMSE score <24

Randomization. Upon confirming eligibility to participate, patients were randomized in the study using a sample randomization procedure. Randomization, prepared by a statistician, using a computer-generated 1:1 allocation of patients to either a control group or an intervention group. A coding scheme (ID#, site, study group), matching with the master list of patient names, as study participant identification was developed. Personally, identifiable data and group

assignments kept separately from other study data. Each site kept the study data in a locked cabinet *and* a password protected and encrypted desktop computer.

- **Control group:** Patients received packets containing study instructions and self-administered questionnaires. They also received the *usual care* throughout the study (6 months). Usual care is defined by the routine outpatient care customary to each VAD center. Many VAD Centers in the US share a similar approach to managing LVADs in outpatient clinics with routine follow-up care and as needed educational support (LVAD care) for patients/caregivers provided by specialized VAD nurses (RNs/NPs). Patients in the control group used the usual LVAD self-management process consisting of the utilization of LVAD system operation manuals and videos and logs for daily care, self-monitoring, and reporting to any of the outpatient VAD RNs/NPs. It is also a common practice for VAD Centers to require patients and/or caregivers to bring their LVAD care logs during routine clinic visits.
- **Intervention group:** Intervention patients performed LVAD self-management (assisted by caregivers as needed) as directed by the VAD Care App¹ and supported by VAD RNs/NPs throughout the process. The app provided the patient with directions in completing the tasks and procedures required for daily LVAD care and management. It also provided an efficient channel of communication between RNs/NPs, patients and/or caregivers for interventions related to abnormal results (e.g., low LVAD flow), making recommendations to correct a deficit in knowledge and skills of LVAD self-management and to address other LVAD care-related issues rapidly. Additionally, the app notified the RNs/NPs with text messages when a patient did not complete self-management for two consecutive days. In addition to receiving the *usual care*, patients in the intervention group had:

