 - a. Completed a study protocol training a day before discharge. First, the CRC downloaded the VAD Care App¹ into an iOS or an Android-compatible smartphone owned by the participant or provided by the study team. Second, the CRC trained the patient and caregiver in the use of the app. Third, the CRC asked the patient and caregiver to demonstrate the use of the app at least twice to ensure proficiency in using the app.
 - b. Received an intervention package consisting of study instructions, self-administered questionnaires, and smartphones with the app ready for use at home.
 - c. Used the app daily for a total of 6 months post-implantation hospital discharge. As prompted by the app, the patient and/or caregiver will implement the LVAD care regimen.
 - d. Completed an "*LVAD knowledge and skill review and evaluation*" at week 1, and months 1 and 5 to facilitate LVAD care self-efficacy and adherence. This review and evaluation were conducted by the VAD RNs/NPs during clinic visits or delivered via a video chat.

Data Collection. Data were collected at baseline (1-2 days before hospital discharge) and 1, 3, and 6 months after implantation hospitalization discharge. Approaches for data collection included reviews of a patient's healthcare/medical record, completion of self-administered questionnaires, and face-to-face interviews. The following data collection tools were used:

- **Demographic and Clinical Profiles.** Common demographic data such as age, sex, race, education, and health history collected from informants (patients and/or caregivers). Clinical profiles included LVAD indication (implant strategy), model, and other pertinent clinical data, including comorbidities and risk stratification in advanced heart failure (INTERMACS Classifications).³ The Charlson Comorbidity Index (CCI), which evaluated 17 different comorbidities assigned to various weights (scores), were also employed. The CCI is a valid and reliable measurement instrument that is widely used for evaluating comorbidity indexes in cardiovascular, cardiac surgery, and LVAD patients.^{4,5}

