- **LVAD Care Self-Efficacy** was measured with a 20-item LVAD Patient Self-Efficacy Scale, used to assess a patient's confidence in managing the challenges presented by the daily LVAD care regimen. The instrument employs a 6-point rating scale ranging from 0 (*not confident at all*) to 5 (*extremely confident*), with standardized sum scores ranging from 0 to 100. High sum scores indicate higher confidence in one's ability to manage the complexity of the regimen. The validity and reliability of the instrument were already established by factorial and convergent validity with a Cronbach's alpha coefficient of 0.92.⁶⁻⁹
- **Adherence** to the LVAD care regimen was measured with the 9-item LVAD Patient Home Management Adherence Scale, used to assess the degree of the patient's consistency in completing the daily LVAD care. The instrument employs a 6-point rating scale, ranging from 0 (*never*) to 5 (*all the time*), with standardized sum scores ranging from 0 to 100. High sum scores indicate high adherence to the regimen. The validity and reliability of the instrument were also established by factorial and convergent validity with a Cronbach's alpha coefficient of 0.95.⁶⁻⁹
- **Complications and Hospital Readmission.** Two separate forms were created for capturing characteristics and frequency of LVAD-related complications and unplanned hospitalization through a monthly review of the patient's medical record(s) and interviews of patients and/or caregivers. These forms consisted of a checklist and tables format, a commonly used approach for collecting complications and healthcare utilization/hospital readmission episodes in heart failure.¹⁰
- **Quality of Life** was measured with the Kansas City Cardiomyopathy Questionnaire (KCCQ). This 23-item instrument used to assess several health-related QOL domains, including physical function, symptoms, social function, among others. The instrument employs a 6-point Likert response scale with sum

scores ranging from 0 to 100. High sum scores indicate better quality of life. The validity, reliability, and sensitivity of the KCCQ have been well established in patients with heart failure and LVADs worldwide.¹¹⁻¹³

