Data Analysis. All data management and statistical analyses performed with REDCap and SAS.^{14,15} Study data were checked for quality and completeness. Data were also checked to ensure that assumptions were met before performing statistical analyses. Descriptive statistics and graphical displays used to summarize the data by the study group. Continuous variables summarized with medians and IQR or means and standard deviations, depending on the distribution. Categorical variables were summarized using percentages and frequencies. Differences in the study group's outcome variables were compared for each period (T0, T1, T2, and T3) with Mann Whitney U tests and chi-square tests set at 0.05 level of significance. Confidence intervals (95%) provided with the summary statistics as well as model estimates and effect size estimates for the next stage of this pilot.

REFERENCES

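### Aim 3 may partly reflect how often complications are noticed, because nurse contact is greater by design in the app arm and no safeguard against unequal detection is described

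*Combined protocol and SAP*

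**What the plan says.** The Purpose section lists complications as the third of five aims. Under Data Collection, two separate forms capture the characteristics and "frequency of LVAD-related complications and unplanned hospitalization through a monthly review of the patient's medical record(s) and interviews of patients and/or caregivers". No arm-specific procedure is given, so I read both sources as applying to both arms.

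Nurse contact does differ by arm. For the intervention group, the Randomization section describes three routes, all on top of usual care:

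- The app supplies "an efficient channel of communication between RNs/NPs, patients and/or caregivers for interventions related to abnormal results (e.g., low LVAD flow").
- It also watches for inactivity: "the app notified the RNs/NPs with text messages when a patient did not complete self-management for two consecutive days".
- Item d schedules a nurse-run review of knowledge and skills at week 1 and months 1 and 5, at a clinic visit or by video.

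Control patients also keep logs and report to the VAD nurses. The protocol adds that centers commonly "require patients and/or caregivers to bring their LVAD care logs during routine clinic visits".

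The Data Analysis section compares the arms at each time point "with Mann Whitney U tests and chi-square tests set at 0.05 level of significance". It promises confidence intervals and effect sizes for the next stage. The text describes no blinded abstraction, no adjudication, no criteria for an LVAD-related complication and no analysis that allows for unequal detection. The forms themselves are not reproduced.

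**The concern.** The app is partly a surveillance system, and complications are an outcome that surveillance helps to find. In the app arm an abnormal reading can reach a nurse through the app, and missed days reach one without the patient having to act. In the control arm the same problem is known once the patient reports it or brings a log to a visit. A problem that a nurse has already dealt with is more likely to be in the record at the next monthly review, or to be known to the patient at interview. That last link is my inference, but it is a plausible one.

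Randomization gives no protection here, because the difference arises after allocation. At stake are the reading of aim 3 and the effect size handed to the next stage. A larger trial with the same capture would narrow the interval without removing the bias.

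**Working it through.** The documents state no event rate, detection rate or power for complications, so there is no figure to reproduce. The check has three steps.

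**1. Routes by which an event can come to notice**

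| Route | Control | App |
|---|---|---|
| Monthly record review | yes | yes |
| Patient or caregiver interview | yes | yes |
| Reporting to nurses and routine visits (usual care) | yes | yes |
| App channel for abnormal results | no | yes |
| Text alert after two missed days | no | yes |
| Nurse reviews, week 1 and months 1 and 5 | no | yes |

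The last three rows are the asymmetry.

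**2. Size of a possible bias**

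Recorded rate ratio = true rate ratio × (detection in app arm ÷ detection in control arm).

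Assumed detection, for illustration only: 90% in the app arm, 70-80% in the control arm.

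- No true effect: 0.90/0.80 = 1.125 (1.13), up to 0.90/0.70 = 1.286 (1.29).
- True 20% reduction: 0.80 × 1.125 = 0.90, up to 0.80 × 1.286 = 1.03.
- Equal detection: the factor is 1 and there is no bias.

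**3. What this could do to the planned test**

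Inputs from the documents: "This study recruited a total of 68 patients" and "computer-generated 1:1 allocation of patients to either a control group or an intervention group", hence 68/2 = 34 per arm (the actual split is not stated); level 0.05; assessments at "1, 3, and 6 months after implantation hospitalization discharge". My assumptions: two-sided test, no losses, outcome taken as at least one recorded complication, Pearson chi-square without continuity correction, and the risks and detection rates below. Recorded risk = true risk × detection in that arm. Rejection probabilities are exact, from full enumeration of two binomials. The detection pairs are a second assumed set, chosen to vary the gap.

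| Detection, control / app | Recorded ratio, no true effect | Chance of a false app-worse result (true risk 0.50 in both arms) | Recorded ratio, true ratio 0.60 | Chance of a significant app-better result (true risks 0.50 vs 0.30) |
|---|---|---|---|---|
| 1.00 / 1.00 | 1.00 | 2.2% | 0.60 | 40.3% |
| 0.90 / 1.00 | 1.11 | 5.6% | 0.67 | 26.0% |
| 0.80 / 0.95 | 1.19 | 8.9% | 0.71 | 17.8% |
| 0.70 / 0.95 | 1.36 | 18.4% | 0.81 | 8.9% |

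For the widest gap, the false app-worse chance is 11.2% at a true risk of 0.30 and 31.1% at 0.70. With 34 per arm and a control risk of 0.50, 80% power needs an app risk of about 0.18, so there is little room for attenuation.

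**The case against.** The case on the other side is substantial.

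- **Two sources, both arms.** Interviews stand beside record review, with no weights and no difference by arm, and they may narrow the gap. A reader might infer that counts come mainly from the record, or that app messages are filed in it. The documents say neither.
- **The extra contact may be smaller than it looks.** Reviews held at clinic visits need not be additional contacts, and their stated content is knowledge and skill. The two-day alert signals missed tasks, not a clinical event. Low flow is given as an abnormal result, not as a complication. Control patients report to VAD nurses too.
- **Direction is not settled.** The channel is meant to resolve problems quickly. A problem resolved that way may never become a complication, which is a true effect, or may go unrecorded, which would favor the app. Reversing the assumed rates in step 2 gives 0.80/0.90 = 0.89 down to 0.70/0.90 = 0.78.
- **Severity may be recorded.** The forms capture characteristics, and hospitalizations have their own form. A reader might infer that all complications are pooled whatever their severity; the text does not say so.
- **This is a pilot**, and complications are one aim of five.

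Most of this stands, and it limits the claim to a possible, unquantified bias. It does not remove the asymmetry, and it does not supply a safeguard. Pilot status cuts both ways, since the estimates are meant for use in the next stage.

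**Conclusion.** The concern holds in conditional form. Unequal nurse contact is a matter of design, and the absence of any described safeguard can be read from the text. Whether detection really differs, and by how much, cannot be known from the documents. The 1.13 to 1.29 range and the table of rejection chances follow from assumed rates and should not be quoted as estimates. Mild outpatient complications are the most exposed. Unplanned hospitalizations are less so, although closer monitoring could itself prompt admissions.

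The stronger reading, that the aim 3 result is biased against the app and hides a benefit, is not supported. It needs more events to be recorded in the app arm because of the extra contact, and nothing in the documents shows this. The point warrants a change because the remedy is specific and cheap, not because a distortion has been demonstrated.

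**What to change.** - Add one field to each of the two existing forms for how the event first came to notice: app alert or message, scheduled nurse review, routine clinic visit, patient call, monthly interview or hospital admission.
- Apply the same written complication criteria and the same interview in both arms.
- Keep the all-complications comparison. Beside it, report a between-arm comparison limited to events least dependent on app contact: death, and complications that led to unplanned hospitalization or to device or surgical intervention.
- Show outpatient-only complications by arm and source, state that their difference may reflect detection, and do not carry it forward alone as the effect size for the next stage.
- Do not add a sensitivity analysis that drops app-prompted admissions. It can remove events from one arm only and so favors the app mechanically.

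The document is written in the past tense, so collection may be complete. In that case, do the restricted analysis from the characteristics already recorded, and carry the source field into the next stage.

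The cost is one field on two forms, written criteria and a few sentences of analysis text, with no extra visits or patients. The downside is statistical: with about 34 patients per arm, the restricted comparison rests on few events and will have wide confidence intervals. That is why it belongs beside the all-complications comparison and does not replace it.

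### For self-efficacy and KCCQ, no named follow-up comparison uses the T0 score the trial already collects; the possible cost is precision, not validity

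*Combined protocol and SAP*

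**What the plan says.** The Data Analysis section of the combined protocol and SAP is the whole analysis plan. The between-group comparisons it names are separate tests at each measurement time: "compared for each period (T0, T1, T2, and T3) with Mann Whitney U tests and chi-square tests set at 0.05 level of significance". T0 appears there as one more time point to be tested. No change from baseline and no baseline covariate is named for T1, T2 or T3.

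The next sentence adds: "Confidence intervals (95%) provided with the summary statistics as well as model estimates and effect size estimates for the next stage of this pilot". It does not say what the model is, what it adjusts for, or which effect measure is meant.

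The Purpose section sets the goal: "This study aimed to obtain preliminary efficacy data of using a mobile phone application". Self-efficacy is scored "with standardized sum scores ranging from 0 to 100", and the KCCQ also runs from 0 to 100.

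Four statements bear on when T0 was taken:
- Inclusion criteria: "Planned hospital discharge within a week of enrollment".
- Randomization: "Upon confirming eligibility to participate, patients were randomized in the study".
- Data Collection: "Data were collected at baseline (1-2 days before hospital discharge) and 1, 3, and 6 months after implantation hospitalization discharge".
- Intervention group, item a: "Completed a study protocol training a day before discharge".

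The packet described for the control group and the package in item b for the intervention group both include self-administered questionnaires.

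**The concern.** With 68 patients, what this pilot can usefully hand on is an effect estimate and its interval. The trial measures self-efficacy and KCCQ before discharge and again at three later visits. If a patient's T0 score predicts the later one, a comparison that ignores it leaves explainable variation in the error term and gives a wider interval than the same data could support. A T0 significance test does not repair this: it compares the arms at baseline and adjusts nothing at follow-up.

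The point is limited to these two scales. Adherence to home care has doubtful meaning as a score taken before the patient has gone home.

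**Working it through.** The plan gives no power, SD, correlation, effect size or sample-size derivation, so there is no figure of its own to reproduce. The check asks how much precision T0 adjustment could add, and when it would do harm.

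**Inputs from the documents:** 68 patients, 1:1 allocation, 0.05 level.

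**Assumptions:** exactly 34 per arm, complete follow-up, two-sided testing, outcome SD of 1, and T0-to-follow-up correlation rho of 0.3, 0.5 or 0.7, with 0 and 0.2 added to show the lower end.

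**Unadjusted mean difference.** Half-width = t(0.975; 66 df) × sqrt(2/34) = 1.9966 × 0.2425 = 0.484 SD.

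**Adjusted for T0 (ANCOVA).** The variance is multiplied by (1 − rho²) and by 1 + 1/(68 − 4) = 1.0156 for estimating the slope, with 65 df. Half-width = 1.9971 × 0.2425 × sqrt((1 − rho²) × 1.0156) = 0.488 × sqrt(1 − rho²). The last column is 68 / ((1 − rho²) × 1.0156).

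| rho | Half-width (SD) | Unadjusted N with the same variance |
|---|---|---|
| 0 | 0.488 | 67 |
| 0.2 | 0.478 | 70 |
| 0.3 | 0.466 | 74 |
| 0.5 | 0.423 | 89 |
| 0.7 | 0.349 | 131 |

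Adjustment narrows the interval once rho exceeds about 0.13. At rho 0 it widens it by 0.488 − 0.484 = 0.004 SD.

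**Power at an assumed 0.5 SD difference** (noncentral t, Mann-Whitney efficiency 0.955): Mann-Whitney 51%, unadjusted t test 53%, adjusted 56%, 64% and 81% at rho 0.3, 0.5 and 0.7. About 2 points of each gap come from rank test versus t test, not from T0.

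**Bounded scores.** A simulation of 20,000 runs assumed a latent mean of 85 and SD of 18, capped at 100, with about 20% of controls at the ceiling. The mean half-width was 6.64 points unadjusted and 6.42, 5.91 and 4.98 adjusted. Coverage of the adjusted interval was 94.7%.

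**Can T0 serve as a covariate?** T0 falls 1 or 2 days before discharge and app training 1 day before, so T0 may precede or follow training. Randomization follows confirmation of eligibility, with discharge planned within a week of enrollment, so T0 may also follow allocation. No blinding is described, so a self-report taken after allocation could reflect knowledge of the assigned arm.

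If T0 followed training, and training raised it by an assumed 0.2 SD in the intervention arm, adjustment would remove rho × 0.2 of the effect: 0.06, 0.10 or 0.14 SD. A true 0.5 SD effect would be estimated as 0.44, 0.40 or 0.36 SD. Adjusted power, including the slope cost, would be 46%, 46% and 53% against 51% for Mann-Whitney. Adjustment would then understate the effect at every rho and lose power at 0.3 and 0.5.

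**The case against.** The strongest objection is that the loss is conditional throughout. It requires a T0-to-follow-up correlation the documents do not give, a T0 score untouched by allocation and training, and an unnamed model that does not already adjust for T0. All of that stands. Self-efficacy for daily home care, rated in hospital, might correlate only weakly with later ratings, and at rho 0.2 the gain is worth about 2 patients. Complete follow-up is also a favourable assumption for the absolute figures: with 27 per arm, adjusted power at rho 0.5 is about 54%, not 64%.

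The timing objection stands too. Questionnaires are listed among the materials each arm received, and in the intervention arm they come after training in the list. That hints that T0 forms may have been filled in after allocation. It does not show it, because the forms could be for follow-up and a list is not a timetable. A reader who infers that T0 was contaminated goes beyond the text, as does one who assumes it was clean.

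Rank tests on bounded scores are a defensible choice in a pilot, and the fix keeps them.

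A reader might infer that the plan's tests are biased or invalid. The documents do not support that: allocation is randomized, and an unadjusted comparison needs no baseline score to be valid. A reader might also infer that T0 was never used in estimation. That is not supported either, since the promised model could include it.

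**Conclusion.** The point holds as one about precision. The named T1 to T3 comparisons of self-efficacy and KCCQ leave out a baseline score the trial already has. Under the stated assumptions, T0 adjustment would cut the half-width from 0.484 SD to 0.423 SD at rho 0.5 and to 0.349 SD at rho 0.7. At rho 0.3 or below the gain is negligible. The power and half-width figures show what is possible; they are not a demonstrated loss in this trial.

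It is tempting to make the unnamed model and effect measure the main defect. That is missing detail, and it matters here only because it leaves open whether T0 is used. The change is worth making because it is cheap and loses almost nothing when T0 proves uninformative, provided the date check is passed. Confidence is medium.

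**What to change.** 1. Check each patient's T0 date against the dates of allocation and app training.
2. If T0 was taken before allocation was known and before training, report for self-efficacy and KCCQ an ANCOVA mean difference with 95% confidence interval (arm and T0 score) at each of T1, T2 and T3, as the effect estimate for the next stage. Keep the Mann-Whitney test as sensitivity analysis.
3. If that order cannot be shown, keep the unadjusted estimate as the lead for the whole trial and show the adjusted one as sensitivity analysis. Apply one rule to both arms, because only one arm is trained.
4. Report T0 by arm descriptively, without a significance test.
5. If the analysis is already done, as the past tense of the document suggests, label the model post hoc and report it beside the Mann-Whitney results.

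The cost is a few sentences in the plan, a few lines of SAS and the date check; no new patient data are needed. The downsides are a linear-model assumption on bounded 0 to 100 scores, for which the rank test is the safeguard, and an interval wider by 0.004 SD if T0 is uncorrelated with follow-up.
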